## 7.9.5 Descriptive Endpoints

Time windows for the following endpoints will be evaluated: visit 2 – visit 7 (Run-in period), visit 7- visit 11 (Auto Basal target set at 120 mg/dL), visit 11- visit 13 (Auto Basal target set at 100 mg/dL), and visit 13 to the end of study (EOS) (Auto Basal target set at investigator's discretion) or exit.

- Time spent in the SmartGuard feature versus time spent in Manual Mode
- Change in mean glucose value from baseline to EOS
- Time in different ranges (% of SG): SG < 54 mg/dL, SG < 70 mg/dL, 70 mg/dL  $\leq$  SG  $\leq$  140 mg/dL, 70  $mg/dL \le SG \le 180 \, mg/dL$ , SG > 140 mg/dL, 180 mg/dL, 250 mg/dL, and 350 mg/dL
- Number of Events, Area Under Curve (AUC) and Time in the hyperglycemic range: SG > 140 mg/dL, 180 mg/dL, 250 mg/dL, and 350 mg/dL
- Number of Events, AUC and Time in the hypoglycemic range: SG < 54 and 70 mg/dL
- Meal/exercise challenge
  - Change in BG values during meal/exercise challenge (BG prior and BG 2 hours after meal/exercise)
  - Change in % of time in euglycemia 70-180 mg/dL during meal/exercise challenge, prior and 2 hours after meal/exercise
  - Difference in AUC during meal challenge prior and 2 hours after meal/exercise
- Change of Total Daily Dose (TDD) of insulin from baseline to EOS
- Change of weight from baseline to EOS
- Subgroup analysis will be performed for:
  - Setpoint
    - 100 mg/dL
    - 110 mg/dL
    - 120 mg/dL
    - 150 mg/dL (Temp Target Usage)
    - Age
- Age 18-80
- Age 7-17

20-DEC-2023 Revision 3.0 Page 24 of 25

**Form** Medtronic

- Age 7-13
- Age 14-17

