#### 8.3 Inclusion Criteria

- 1. Age 7-80 years at time of screening.
- 2. Has a clinical diagnosis of type 1 diabetes:
  - a. 14–80 years of age: A clinical diagnosis of type 1 diabetes for 2 years or more as determined via medical record or source documentation by an individual qualified to make a medical
  - b. 7–13 years of age: A clinical diagnosis of type 1 diabetes for 1 year or more as determined via medical record or source documentation by an individual qualified to make a medical diagnosis.
- 3. Does not require a legally authorized representative to consent on their behalf due to mental or intellectual disability.
- 4. Subject or parent/caregiver is literate and able to read the language offered in the pump or pump materials.

D00409632 Version E Page 48 of 106

- 5. Subject and/or legally authorized representative is willing to provide informed consent for participation.
- 6. Is willing to perform fingerstick blood glucose measurements as needed.
- 7. Is willing to wear the system continuously throughout the study.
- 8. Must have a minimum daily insulin requirement (Total Daily Dose) of greater than or equal to 8 units and a maximum total daily dose of 250 units or less.
- 9. Has a Glycosylated hemoglobin (HbA1c) less than 10% (as processed by Central Lab) at time of screening visit.

Note: All HbA1c blood specimens will be sent to and tested by a National Glycohemoglobin Standardization Program (NGSP) certified Central Laboratory. HbA1c testing must follow NGSP standards.

- 10. Has thyroid-stimulating hormone (TSH) in the normal range OR if the TSH is out of normal reference range, the Free T3 is below or within the lab's reference range and Free T4 is within the normal reference range.
- 11. Uses pump therapy for greater than 6 months (with or without CGM experience) prior to screening
- 12. Is willing to upload data from the study pump, must have Internet access, and a computer system, or compatible smartphone that meets the requirements for uploading the study pump.
- 13. Is willing to take one of the following insulins and can financially support the use of either of the 2 insulin preparations as required during the run-in period:
  - a. Humalog (insulin lispro injection)
  - b. NovoLog (insulin aspart injection)
  - c. Admelog (insulin lispro injection)
- 14. Is willing to take Lyumjev insulin during the study period (supplied via Sponsor).

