**Table 3. Study Visit Details** 

			Run-In	Period					Study Period			
	Visit 1 (Office)	Visit 2 (Office)	Visit 3** and 4** (Phone)	Visit 5 (Phone)	Visit 6 (Office or Virtual Office)	Visit 7 (Office)	Visit 8** (Phone)	Visit 9, 10 & 11 (Phone)	Visit 12 (Office)	Visit 13 (Office)	Visit 14 (Office)	Visit 15* (Office)
Visit Window	Enrollment		Day 1 and Day 3 after Visit 2	Day 7 (±2 days) after Visit 2	Day 14 (±3 days) after Visit 2	Day 7 (-7 days) after Visit 6	Day 2 after Visit 7	Day 7 (±2 days), Day 14 (±3 days), and Day 21 (±3 days) after Visit 7	Day 28 (+7 days) after Visit 7	Day 44 (±3 days) after Visit 7	Day 60 (+7 days) after Visit 7	Day 90 (+7 days) after Visit 7 EOS
Visit Activities and Data Collection												
Collect consent forms, e.g., ICF, Assent form (if applicable), California Experimental Subject's Bill of Rights (if applicable), HIPAA form and forms required by local regulation	X											
Assess subject eligibility to participate in the study	Х											
Measure subject height and weight Note: Body mass index (BMI) will be calculated automatically in the study database, based on height and weight measurements entered.	Х											Х
Collect demographic and other baseline characteristics according to eCRF questions	Х											
Collect urine test for pregnancy from female subjects of child-bearing age or capability (Point of Care or local lab)	Х											
Collect blood sample for HbA1c testing (all subjects). All collected blood specimens will be sent to and tested by a NGSP certified Central Laboratory. HbA1c testing must follow NGSP standards.	х											х
Collect blood sample for HbA1c testing (Subjects 21 years of age and older). All collected blood specimens will be						Х			Х		Х	

Version E D00409632

Page 56 of 106

			Run-In	Period					Study Period			
	Visit 1 (Office)	Visit 2 (Office)	Visit 3** and 4** (Phone)	Visit 5 (Phone)	Visit 6 (Office or Virtual Office)	Visit 7 (Office)	Visit 8** (Phone)	Visit 9, 10 & 11 (Phone)	Visit 12 (Office)	Visit 13 (Office)	Visit 14 (Office)	Visit 15* (Office)
Visit Window	Enrollment		Day 1 and Day 3 after Visit 2	Day 7 (±2 days) after Visit 2	Day 14 (±3 days) after Visit 2	Day 7 (-7 days) after Visit 6	Day 2 after Visit 7	Day 7 (±2 days), Day 14 (±3 days), and Day 21 (±3 days) after Visit 7	Day 28 (+7 days) after Visit 7	Day 44 (±3 days) after Visit 7	Day 60 (+7 days) after Visit 7	Day 90 (+7 days) after Visit 7 EOS

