#### **Determination of Sample Size** 6.

## 6.1 Sample Size and Investigational Centers

A total of up to 250 subjects with insulin-requiring type 1 diabetes age 7-80 will be enrolled at up to 25 investigational centers across the United States in order to have at least 200 subjects enter the study period. Up to 125 subjects will be enrolled in the pediatric age group (7-17 years of age) and up to 125 in the adult age group (18 years or older):

Subject Age Group	ect Age Group Sub-groups	
Pediatric	All Pediatric	Minimum 100 Subjects
Age 7 – 17 years	Age 7 - 13 years	Minimum 20 Subjects
	Age 14 - 17 years	Minimum 20 Subjects
Adult Age 18 - 80 years	N/A	Minimum 100 Subjects

A minimum of 10 subjects and a maximum of 40 subjects is targeted for enrollment at each investigational center to ensure that the results from the individual investigational center may be pooled for analysis.

Investigational centers will be encouraged to enroll a study population that represents a wide variety of backgrounds.

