# 7.6 Demographic and Other Baseline Characteristics

Subject characteristics, including age, gender, race, ethnicity, medical diagnosis, height, weight, Body Mass Index (BMI), and baseline HbA1c will be summarized by descriptive statistics (mean, standard deviation, minimum, median, and maximum) for continuous variables and by counts and percentages for categorical variables.

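### Pediatric weight and total daily insulin changes are planned without any scaling for growth or body size, so the weight change in ages 7-17 cannot be read against the listed Lyumjev risk of weight gain

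*SAP*

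**What the plan says.** SAP 7.9.5 lists two descriptive endpoints: "Change of Total Daily Dose (TDD) of insulin from baseline to EOS" and "Change of weight from baseline to EOS". Protocol 4.2.4 and 14.4.2 list the same two. None of these places mentions units per kilogram, change in BMI, a percentile, a z-score or a growth reference. SAP 7.9.5 asks for results in ages 18-80, 7-17, 7-13 and 14-17.

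No unit is named for either endpoint. Where TDD appears as an eligibility limit (Protocol 8.3), it is in absolute units: "greater than or equal to 8 units and a maximum total daily dose of 250 units or less".

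Protocol Table 3 has the line "Measure subject height and weight", marked at Visit 1 and Visit 15 only, with the note "Body mass index (BMI) will be calculated automatically in the study database". The SAP uses BMI in two places: the baseline summary in 7.6 ("height, weight, Body Mass Index (BMI), and baseline HbA1c will be summarized by descriptive statistics") and as a covariate in the HbA1c imputation model in 7.4. Neither document plans a change in BMI.

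The study is single arm (SAP section 5), with a minimum of 100 and a maximum of 125 subjects aged 7-17 (SAP 6.1). Protocol 10.1 includes weight gain among the risks of Lyumjev.

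**The concern.** Children gain weight over four months whatever insulin they use, and if the dose per kilogram stays the same their units per day rise with body mass. With no control arm, no other children in the study show the background gain. The age subgroups separate children from adults, but they only isolate the affected numbers; they do not correct them.

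At stake is how a pediatric weight table is read. Weight gain is a listed Lyumjev risk, so a reader will naturally set the pediatric mean change beside it. A positive mean could be growth, treatment or both, and the planned summary offers no way to tell. The height needed to tell them apart more clearly is already being collected.

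**Working it through.** **1. The interval.** Visits 1 to 6 take up to 30 days, and Visit 15 is 90 days after Visit 7. So 30 + 90 = 120 days, which matches the stated participation of about 120 days. A 7-day gap from Visit 6 to Visit 7 and the +7-day window at Visit 15 give at most 30 + 7 + 97 = 134 days. Visit 2 to Visit 15 is at least 11 + 0 + 90 = 101 days, so the weight interval is no shorter than that.

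**2. Growth in weight.** Assumption: 2 to 6 kg per year at ages 7-17. Gain = rate × days / 365.25.
- 120 days: 2 × 120/365.25 = 0.66 kg; 6 × 120/365.25 = 1.97 kg.
- 101 days at 2 kg/year: 0.55 kg. 134 days at 6 kg/year: 6 × 134/365.25 = 2.20 kg.
- Part before Lyumjev starts at Visit 7 (30 of the 120 days): 0.16 to 0.49 kg. With weight taken only at Visits 1 and 15, the time windows in SAP 7.9.5 cannot separate this part.

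**3. Would it show?** Half-width of the 95% CI = t(0.975, n-1) × SD/√n, with an assumed SD of weight change of 1.5 to 3 kg.
- n = 100: 1.984 × 1.5/10 = 0.30 kg; 1.984 × 3/10 = 0.60 kg. Even the low-end gain of 0.66 kg exceeds this.
- n = 80: 0.33 to 0.67 kg. At the largest SD the low-end gain is about equal to the half-width; otherwise it is clearly above it.

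**4. Would a height-based measure remove it?** Weight gain at constant BMI = w × ((h + dh)²/h² - 1). Assume height growth of 5 to 7 cm per year, so dh = 1.6 to 2.3 cm in 120 days.

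| Assumed height, weight | Gain at constant BMI |
|---|---|
| 130 cm, 28 kg | 0.71 to 1.00 kg |
| 145 cm, 40 kg | 0.91 to 1.28 kg |
| 160 cm, 52 kg | 1.07 to 1.51 kg |

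Height growth alone thus yields gains of the same order as step 2. A BMI-based measure absorbs this part, and an age- and sex-standardised one also allows for normal change in BMI with age.

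**5. TDD.** Growth-driven change = growth in kg × dose per kg, assuming a constant 0.6 to 1.0 U/kg/day.
- 120 days: 0.66 × 0.6 = 0.4 U/day to 1.97 × 1.0 = 2.0 U/day.
- If baseline is a 21-day run-in and follow-up is Visit 13 to EOS (days 44 to 90), the midpoints are 10.5 + 67 = 77.5 days apart. The growth part is then 2 × 77.5/365.25 × 0.6 = 0.25 U/day to 6 × 77.5/365.25 × 1.0 = 1.27 U/day.

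This is only one component. At Visit 7 every subject changes insulin and turns Auto Correction on. All except prior Medtronic Auto Mode users also move from Manual Mode to SmartGuard. Table 3 changes the meal-bolus timing instruction as well.

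**The case against.** The strongest reply is that nothing is decided on these endpoints. They lie outside the fixed testing sequence (SAP 7.5) and the pass/fail rule (SAP 7.9.1), and weight is not among the safety items in SAP 7.9.6 or 7.10. A raw weight change correctly describes what was measured, adults are reported separately, and BMI change could be derived later. This limits the importance of the point. It does not make the pediatric weight change interpretable: adults are not a growth control, and a measure left to be derived later is not prespecified.

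Other parts of the reply stand:
- **Units.** A reader might take absolute units as stated in the plan. They are not. SAP 7.2 places table templates in a separate document that is not available here. Absolute change is the plain reading because no scaled version appears in either document.
- **TDD.** A reader might infer that pediatric TDD will rise whatever the insulin does. The documents do not support that. The baseline is undefined and several influences change together at Visit 7, so the direction is unknown. Scaling per kilogram would not isolate an insulin effect either.
- **Labeling.** A reader might infer a biased pediatric label. The documents say only that the study supports product and system labeling. They plan no pediatric statement on weight or insulin requirement, and nothing ties the risk entry in Protocol 10.1 to this endpoint.
- **Magnitude.** The growth rates, the SDs and the dose per kilogram are all outside assumptions.

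**Conclusion.** The point holds for weight as a minor reporting weakness. The planned pediatric weight change mixes growth with any treatment effect and includes time before Lyumjev. Under an assumed 2 to 6 kg per year, growth contributes about 0.7 to 2.0 kg over 120 days, enough in nearly all the cases examined to appear as a clear mean gain with no drug effect. For TDD the conclusion is narrower: growth pushes units per day upward by roughly 0.25 to 2.0 U/day under the stated assumptions, within a net change whose direction the documents do not establish. No primary or secondary conclusion is affected.

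**What to change.** In SAP 7.9.5, for ages 7-17 and the 7-13 and 14-17 subgroups:
- Add the change in BMI-for-age (or weight-for-age) z-score from Visit 1 to Visit 15, against a named age- and sex-specific growth reference. Keep raw weight change beside it rather than replacing it.
- Report TDD change also in units/kg/day, using Visit 1 weight for baseline and Visit 15 weight for EOS.
- State the TDD baseline window, and note that per-kilogram scaling removes only the growth part of the change.

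The cost is SAP wording, the choice of a growth reference (neither document names one) and a few derived variables from age, sex, height and weight. No procedure, visit or hypothesis changes. Subjects without Visit 15 height or weight, for example after a virtual visit, drop out of this summary; those without weight are already lost to the raw weight change. Report the number contributing.

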## 7.9.6 Safety Data Summarized

Time windows for the safety data will be evaluated: visit1-visit2, visit 2 - visit 7, visit 7 to the end of study (EOS) or exit, and visit 13 to the end of study (EOS) or exit.

- Serious Adverse Events (SAE)
- Serious Adverse Device Effects (SADE)
- Unanticipated Adverse Device Effects (UADE)
- Incidence of Severe Hypoglycemia
- Incidence of Severe Hyperglycemia
- Incidence of DKA

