## **Study Period:**

- Visit 7 (Office/Virtual Office): Start Study Period with Lyumjev insulin Day 7 (-7 days) after Visit 6
  - Ask subjects and their parents/caregivers (if applicable) about adverse events, device performance, unexplained hyperglycemia and insulin infusion related issues with Lvumiev insulin
  - HbA1c for subjects 21 and older
  - Review CareLink reports
  - Start Auto Basal target at 120 mg/dL setpoint with Active Insulin Time set to 4 hours, titrate towards 2-3 hours or at investigator's discretion
  - Turn on SmartGuard with Auto Corrections "ON"

D00409632 Version E Page 53 of 106

- Instruct subjects about the required meal and exercise challenges for both the 100 mg/dL and 120 md/dL setpoint between visits 9 and 13 of the study period
- Visit 8 (Phone): Day 2 after Visit 7 Required for subjects without CGM or closed loop experience; as needed for all others
  - Adjust pump settings as needed
  - Ask subjects, their parents/caregivers (if applicable), and companions, if they require assistance, e.g., additional training
  - Ask subjects and their parents/caregivers (if applicable) about adverse events, device performance, unexplained hyperglycemia and insulin infusion related issues with Lyumjev insulin
  - Review CareLink reports
  - o Remind subjects about meal/exercise challenges for 120 mg/dL setpoint
- Visit 9 (Phone): Day 7 (±2 days) after Visit 7
  - o Adjust pump settings as needed
  - Ask subjects and their parents/caregivers (if applicable) about adverse events, device performance, unexplained hyperglycemia and insulin infusion related issues with Lyumjev insulin
  - o Review CareLink reports
  - o Remind subjects about meal/exercise challenges for 120 mg/dL setpoint
- Visit 10 (Phone): Day 14 (±3 days) after Visit 7
  - Adjust pump settings as needed
  - Ask subjects and their parents/caregivers (if applicable) about adverse events, device performance, unexplained hyperglycemia and insulin infusion related issues with Lyumjev insulin
  - Review CareLink reports
  - o Remind subjects about meal/exercise challenges for 120 mg/dL setpoint
- Visit 11 (Phone): Day 21 (±3 days) after Visit 7
  - Adjust pump settings as needed
  - Ask subjects and their parents/caregivers (if applicable) about adverse events, device performance, unexplained hyperglycemia and insulin infusion related issues with Lyumiev insulin
  - Review CareLink reports

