  - Change Auto Basal target to 100 mg/dL setpoint with Active Insulin Time set to 2-3 hours or at investigator's discretion
  - Remind subjects about meal/exercise challenges for 100 mg/dL setpoint
- Visit 12 (Office/Virtual Office): Day 28 (+7 days) after Visit 7
  - Adjust pump settings as needed
  - Ask subjects and their parents/caregivers (if applicable) about adverse events, device performance, unexplained hyperglycemia and insulin infusion related issues with Lyumjev insulin
  - HbA1c for subjects 21 and older
  - Review CareLink reports
- Visit 13 (Office/Virtual Office): Day 44 (±3 days) after Visit 7
  - Adjust Auto Basal target with Active Insulin Time at investigator's discretion
  - Ask subjects and their parents/caregivers (if applicable) about adverse events, device performance, unexplained hyperglycemia and insulin infusion related issues with Lyumjev insulin
  - **Review CareLink reports**

- o Remind subjects about meal/exercise challenges
- Visit 14 (Office/Virtual Office): Day 60 (+7 days) after Visit 7
  - o Adjust pump settings as needed
  - o Ask subjects and their parents/caregivers (if applicable) about adverse events, device performance, unexplained hyperglycemia and insulin infusion related issues with Lyumjev insulin
  - o HbA1c for subjects 21 and older
  - o Review CareLink reports
- Visit 15 (Office/Virtual Office): Day 90 (+7 days) after Visit 7
  - o Ask subjects and their parents/caregivers (if applicable) about adverse events, device performance, unexplained hyperglycemia and insulin infusion related issues with Lyumjev insulin
  - Review CareLink reports
  - Return study devices
  - HbA1c for all subjects
  - End of Study (EOS)

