#### 11. Adverse Events

#### 11.1 Adverse Events

Throughout the course of the study, investigational centers will make all efforts to remain alert to possible reportable adverse events (AEs) or untoward findings. The study personnel will elicit reports of AEs from the subject at each visit (including phone calls) starting at the time of signing the informed consent documenting the medical diagnosis, date of event start and end, causality (relationship to device or procedure), treatment, outcome, assessment of seriousness, and description that includes the details of the event.

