### Safety Considerations with the Use of Lyumjev insulin:

Sites will send out an email to each subject during weeks where no visit is scheduled to inquire about insulin infusion with Lyumiev insulin. The email will ask subjects whether or not they have experienced any insulin infusion reactions with the use of the Lyumjev insulin. The email will also remind subjects that sites should be called if any issues with Lyumjev insulin infusion occur. During such calls, photos and video should be used, if possible.

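### Scheduled adverse-event questioning thins from run-in to the Lyumjev windows of SAP 7.9.6, and the email sent in weeks without a visit does not fill the gap

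*SAP*

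**What the plan says.** **How AEs are found.** Protocol 11.1 states: "The study personnel will elicit reports of AEs from the subject at each visit (including phone calls". Start and end dates are to be documented, and 11.3 requires all AEs during enrollment to be recorded.

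**When subjects are asked.** In the Study Period list of Protocol 9.1.1, contacts are close together at first: "Visit 8 (Phone): Day 2 after Visit 7 Required for subjects without CGM or closed loop experience; as needed for all others"; "Visit 9 (Phone): Day 7 (±2 days) after Visit 7"; "Visit 10 (Phone): Day 14 (±3 days) after Visit 7"; "Visit 11 (Phone): Day 21 (±3 days) after Visit 7". Visits 12 and 13 follow at Days 28 and 44. After that only Visit 14 (Day 60, +7) and the final visit remain: "Visit 15 (Office/Virtual Office): Day 90 (+7 days) after Visit 7". In run-in, Visits 5, 6 and 7 apply to everyone. Visits 3 and 4 are mandatory only for subjects without CGM or closed-loop experience.

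**What happens between visits.** Sites email subjects in weeks with no visit. SAP 5, under the Lyumjev safety considerations, gives the content: "The email will ask subjects whether or not they have experienced any insulin infusion reactions with the use of the Lyumjev insulin". The email's reminder to call is likewise limited to Lyumjev infusion issues. The protocol has the same text.

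**How events are summarized.** SAP 7.9.6 lists SAE, SADE, UADE, severe hypoglycemia, severe hyperglycemia and DKA for four windows: Visit 1-2, Visit 2-7, and "visit 7 to the end of study (EOS) or exit, and visit 13 to the end of study (EOS) or exit". It names no patient-time denominator, although Protocol 12.2 has the DMC review rates per 100 patient-years.

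**The concern.** The windows differ in length and in how often subjects are asked. The study has a single arm, so a reader of the safety tables will naturally set run-in (the subject's own insulin) against the Lyumjev windows. If some events go unmentioned when the next question is weeks away, the sparsely questioned windows will show fewer events at the same true rate, in Lyumjev's favor. The DMC's event rates, which it may compare with external reference rates, would be lowered too.

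The exposed outcomes are those that can begin and end at home. Under Protocol 11.2, severe hyperglycemia turns on BG above 300 mg/dL with ketones above 1.5 mmol/L and/or nausea, vomiting or abdominal pain. Protocol 9.5.2 has ketone results reported by the subject. Under 11.3, ordinary highs and lows are not reported, so classifying an event depends on details that the subject must supply. Severe hypoglycemia treated by a companion is similar.

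**Working it through.** The documents give no contact rate, so there is no stated figure to reproduce. Inputs are the nominal visit days in Protocol 9.1.1, counting contacts after the window opens up to and including its last visit.

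**1. Contacts per 30 days** = 30 × contacts / days.
- Run-in (Visit 2-7, 21 days): 3 contacts (Visits 5, 6, 7) give 30 × 3/21 = 4.3. With Visits 3 and 4, 30 × 5/21 = 7.1.
- Visit 7-EOS (90 days): Visits 9-15 give 30 × 7/90 = 2.3. With Visit 8, 30 × 8/90 = 2.7.
- Visit 13-EOS (46 days): Visits 14 and 15 give 30 × 2/46 = 1.3. The visit windows move this between 1.07 and 1.40.

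Run-in is therefore questioned 3.3 to 5.5 times as often as Visit 13-EOS ((3/21)/(2/46) and (5/21)/(2/46)). Visit 7-EOS is questioned 1.8 to 2.0 times as often ((7/90)/(2/46) and (8/90)/(2/46)).

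**2. Days followed by an AE question within 7 days** = sum of min(gap, 7) / days.
- Run-in, gaps 7, 7, 7: 21/21 = 100%.
- Visit 7-EOS, gaps 7, 7, 7, 7, 16, 16, 30: 49/90 = 54%.
- Visit 13-EOS, gaps 16, 30: 14/46 = 30%.

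**3. Longest gap.** Visit 14 falls on Days 60-67 and Visit 15 on Days 90-97, so they are 90 − 67 = 23 to 97 − 60 = 37 days apart.

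**4. Weeks covered only by the email.** Counting weeks from Visit 7, those beginning on Days 49, 63, 70 and 77 have no visit: four weeks after Visit 13.

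**5. What this could do to counts (assumptions, not in the documents).** Suppose that an event not yet reported is lost with a constant half-life h until the next contact. Capture over a gap g is then (1 − 2^(−g/h)) / (g × ln 2 / h), averaged over the window's days. For Visit 13-EOS at h = 30 days: 43.28 × [(1 − 2^(−16/30)) + (1 − 2^(−1))] / 46 = 0.76.

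| h (days) | Run-in | Visit 7-EOS | Visit 13-EOS | Visit 13-EOS / Visit 7-EOS | Visit 13-EOS / run-in |
|---|---|---|---|---|---|
| 14 | 0.85 | 0.68 | 0.58 | 0.85 | 0.69 |
| 30 | 0.92 | 0.83 | 0.76 | 0.92 | 0.82 |
| 90 | 0.97 | 0.94 | 0.91 | 0.97 | 0.93 |
| 180 | 0.99 | 0.97 | 0.95 | 0.99 | 0.97 |
| 365 | 0.99 | 0.98 | 0.98 | 0.99 | 0.98 |

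A simpler assumption is that 30% of events with no AE question within a week go unreported. Capture is then 100% in run-in, 0.544 + 0.7 × 0.456 = 86% in Visit 7-EOS, and 0.304 + 0.7 × 0.696 = 79% in Visit 13-EOS.

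**6. Scale in events.** Protocol Table 5 gives a reference severe-hyperglycemia rate of 71.64 per 100 patient-years for age under 15. If that applied to 100 pediatric subjects over 46 days, 71.64 × 46/365.25 ≈ 9 events would be expected. A 21% loss would remove about 2.

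**The case against.** A reader might infer that counts must fall with time on Lyumjev because of the schedule alone. The documents do not support that. No day drops out of questioning: Visits 14 and 15 are AE visits, all AEs are recorded with dates, and an event on Day 70 can be reported at Day 90 and placed in its window. Sparser visits lengthen recall; a fall in counts also needs forgotten or unreported events.

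Other routes also continue after Visit 13. Table 3 has subjects told to call about any change in health, pump data uploaded weekly or continuously, and CareLink reports reviewed at visits. It also has subjects asked about unexplained hyperglycemia at each study-period visit and reminded to bring the ketone meter to office visits. Protocol 13 has technical-support call reports screened for AEs. SAEs and facility-treated DKA are unlikely to be forgotten in 23-37 days.

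A reader might also contrast Visits 7-13 (5/44 or 6/44 days, 3.4-4.1 per 30 days) with the 1.3 after Visit 13. SAP 7.9.6 has no Visit 7-13 window, so the contrast it displays on Lyumjev is 2.3-2.7 against 1.3, with the later window nested in the earlier. Run-in is tabulated, but it differs in insulin and, for most therapy groups, in pump mode. The windows are descriptive, and pass/fail (SAP 7.9.1) rests on HbA1c and time in range.

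All of that stands, and it narrows the point without removing it. Uploads show glucose, not symptoms or need for assistance. The call instruction specific to unexplained hyperglycemia is marked only at Visits 2 and 7. Technical support sees only those who call.

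**Conclusion.** The thinning is a matter of record: 4.3-7.1, 2.3-2.7 and 1.3 scheduled AE contacts per 30 days, and 100%, 54% and 30% of days with an AE question inside a week. The between-visit email does not compensate, because it covers infusion reactions only.

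Under-counting is possible, not established. Under the half-life assumption, Visit 13-EOS captures 85-92% as much as Visit 7-EOS for half-lives of 14-30 days, and 97-99% for 90 days or more. Against run-in the figures are 69-82% and 93-98%. The model ignores the parallel routes, so it describes only events that depend on being asked: severe hyperglycemia and severe hypoglycemia treated at home. Any bias runs one way, making the Lyumjev windows look safer than run-in. No planned test or success criterion is affected. This is a worthwhile, inexpensive improvement in ascertainment, not a flaw that invalidates the safety summary.

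**What to change.** 1. **Email (Protocol synopsis and section 5; SAP 5).** Add the AE question already asked at visits: any severe low, any BG above 300 mg/dL with ketones or symptoms, DKA, or other change in health. Widen the existing reminder to call the site to match. Each week from Visit 7 to Visit 15 would then carry an AE question. Contacts in consecutive seven-day blocks are at most 13 days apart, against up to 37 now, and sites would learn of events sooner.
2. **SAP 7.9.6.** Report events per patient-time in each window, in line with the DMC's rates per 100 patient-years. Show the scheduled contact frequency beside each window and state that differences between windows are read with it.

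**Cost.** One more question in an email already sent, a protocol amendment to its text, occasional follow-up calls and slightly higher reported counts; no added visits. The email change is what evens out ascertainment, and it helps only while subjects are in follow-up. The SAP text alone would only make the imbalance visible.
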